9.3. Adverse Event Reporting Period

AEs reporting period for this trial begins upon subject enrolment in the trial (after signature of informed consent) and ends at the Follow-Up Visit.

All AEs that occur during the AE reporting period specified in the protocol must be reported to DNDi, whether or not the event is considered medication related.

In addition, any AE that occurs subsequent to the AE reporting period that the Investigator assesses as related (ie, reasonable possibility of causal relationship) to the investigational medication should also be reported as an AE.

9.4. Procedures for Dealing With Serious Adverse Events

All SAEs are to be reported **immediately (within 24 h of awareness of SAE by the Investigator)** to the Sponsor Medical Expert and Sponsor Clinical Project Manager by telephone, and also using the serious adverse event (SAE) form sent to: [contact] (copy to the team members indicated in the Safety Management Plan). This includes a description of the event, onset date and seriousness criteria duration, severity, causal relationship to study drug, outcome, measures taken and all other relevant clinical and laboratory data.

The initial report is to be followed by submission of additional information (follow-up SAE form) as it becomes available. Any follow-up reports should be submitted as soon as possible, and if possible within 5 working days of knowledge.

SAE should also be reported on the clinical trial AE page of CRF. It should be noted that the form for reporting of SAE (SAE form) is not the same as the AE section of the CRF. Where the same data are collected, the two forms must be completed in a consistent manner, and the same medical terminology should be used.

In the event of any SAE which, in the investigator's opinion, justifies termination or modification of the trial, dosing will be stopped and the Sponsor Medical Expert and Sponsor Clinical Project Manager will be informed immediately (within 24 h of the investigator becoming aware of the event) by telephone, and the SAE form sent to: [contact] (copy to the team members indicated in the Safety Management Plan.)

In addition to immediately reporting SAEs to DNDi, the investigator will notify the main Research Ethics Committee (REC) of serious adverse events that occur during this trial, if applicable, in accordance with the standard operating procedures issued by the National Research Ethics Service (NRES).

Expectedness: DNDi is responsible for determining the expectedness of the adverse event, using the reference safety information in the Investigator's Brochure. DNDi will notify the Medicines and Healthcare products Regulatory Agency (MHRA) and the European Medicines Agency (EMA) of all suspected unexpected serious adverse reactions (SUSARs), and will be responsible for ensuring that the main REC is notified of SUSARs, if applicable.

- SUSARs that are fatal or life-threatening must be notified to the MHRA/EMA and REC within 7 days after DNDi becomes aware of the event.
- Other SUSARs must be reported to the REC and MHRA within 15 days after DNDi becomes aware of the event.

9.5. Procedures for Handling Withdrawals due to Adverse Events

The investigator will assess the reason for study withdrawal as far as possible and will fully record the circumstances and medical details in the CRF.

Provided that subjects give written informed consent, they will undergo the standard medical examination and laboratory tests at withdrawal from the trial which they would have undergone had they continued participation in the trial (see also Sections 8.13 and 15)

9.6. Exposure in utero

Not applicable

9.7. Adverse Event Follow Up

All AEs should be followed until they are resolved or the Investigator assesses them as chronic or stable or the subject participation in the trial ends (ie, until a final report is completed for that subject, in the case of SAEs).

In addition, all SAEs and those non-serious events assessed by the Investigator as related (i.e. reasonable possibility of causal relationship) to the investigational drug must continue to be followed even after the subject participation in the trial is over. Such events should be followed until they resolve or until the Investigator assesses them as "chronic" or "stable." Resolution of such events is to be documented in source documents and on the CRF.

10. Data Analysis and Statistical Methods

Detailed methodology for summary and statistical analyses of the data collected in this study will be documented in a Statistical Analysis Plan. This document may modify the plans outlined in the protocol; however, any major modifications of the primary endpoint definition and/or its analysis will also be reflected in a protocol amendment. Each part of the study (Part 1 and Part 2) will be reported separately. The Statistical Analysis Plan for each part will be prepared before database lock for that part.

10.1. Sample Size Determination

A sample size of up to 80 subjects (ie, up to 8 per cohort, Table 2) will be considered sufficient to examine the safety and tolerability of emodepside as well as the PK after single oral administration of the investigational drug.

Assuming a screen failure rate of approximately 50%, a total of 144 subjects will need to be screened for inclusion into this study.

For evaluation, a minimum number of 6 evaluable subjects per cohort is required.

In each cohort of up to 8 subjects, 6 are randomised to emodepside and 2 are randomised to placebo.

10.2. Definition of Study Populations Included in the Analysis

The following population sets will be identified:

- Safety Population: All subjects who received at least one dose of IMP.
- PK Concentration Population: All subjects who received at least one dose of IMP and for whom a pharmacokinetic sample has been analyzed.
- PK Parameter Population: All subjects in the PK Concentration Population for whom pharmacokinetic parameters can be derived.

In all populations, treatment will be assigned based upon the treatment subjects actually received, regardless of the treatment to which they were randomized.

Final definition of the study populations will be put in the statistical analysis plan (SAP).

General considerations for data analyses: The minimum set of summary statistics for numeric variables will be: n, mean, standard deviation (or standard error),

median, minimum, and maximum. 95% confidence intervals will be presented where appropriate for data interpretation.

Categorical data will be summarised in frequency tables with n and percentage. Summaries of a categorical variable will include all recorded values.

The minimum and maximum values will be presented to the same number of decimal places as the raw data collected on the CRF (or to 3 significant figures for derived parameters). The mean, median and percentiles (eg, Q1, and Q3) will be presented to one additional decimal place. The standard deviation and standard error will be presented to 2 additional decimal places.

In each part of the study, placebo subjects will be pooled across cohorts taking into account formulation and fed/fasted status.

Out-of-range laboratory tests may be repeated. If a test is out of-range at baseline and repeated before dosing, the latest repeat value before dosing will be used as baseline. However, if a test is out-of-range and repeated at any other time during the study, the out-of-range value (not the repeat value) will be included in statistical summaries.

10.3. Subject Disposition

The disposition of all subjects in the safety population will be summarized including: number of subjects randomized; number completing the study, by treatment; and number discontinued from the study. The number of subject in each analysis population will be summarized by treatment

All subjects who withdraw or are withdrawn from the study will be listed, by treatment, with the reason for withdrawal.

10.4. Efficacy Analysis

Not Applicable

10.6. Pharmacodynamic Analysis

Pharmacodynamic variables at each planned assessment, and change in pharmacodynamic variables from baseline at each planned post baseline assessment, will be summarised by actual treatment.

10.7. Demographics and Other Baseline Characteristics

Demographic and baseline characteristics (eg physical examination, vital signs, weight and ECGs) will be summarised.

Subjects who take concomitant medication will be listed.

10.8. Safety Analysis

Safety and tolerability data will be summarized using the following parameters:

- Vital signs;
- 12-lead ECG;
- Hematology;
- Clinical chemistry;
- Urinalysis;
- Physical and neurological examination;
- AEs.
- Ophthalmology assessments (Part 2, Cohort 10)

No formal hypothesis testing of these parameters will be carried out.

10.8.1. Vital Signs and 12-Lead ECG Safety Parameters

Vital signs at each planned assessment, and change in vital signs from baseline at each planned post baseline assessment will be summarised by actual treatment.

Vital signs of potential clinical importance will be listed separately.

QT interval will be corrected using Bazett's (QTcB) and Fridericia's (QTcF) formulae. Triplicate ECG measurements will be made at some timepoints on Day -1 and Day 0, the mean of the three measurements for each subject will be used at each timepoint.

ECG variables will be summarised by treatment and time point. Differences from baseline will be summarised by treatment and time point.

QTcB or QTcF > 450 msec and increases in QTcB or QTcF from baseline of > 30 msec will be considered to be potentially clinically important. The number of subjects with a potentially clinically important QTcB or QTcF will be summarised by actual treatment and time point, giving the numbers of subjects with QTcB or QTcF > 450 msec, > 480 msec and > 500 msec, and the numbers of subjects with increases in QTcB or QTcF from baseline of > 30 msec and >60 msec. A supporting listing of all subjects with an ECG value of potential clinical importance, and a separate listing of ECG findings classified as abnormal by the investigator, will also be provided.

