After a single oral application of emodepside to rats no biologically relevant effect on respiratory parameters was noted (10-100 mg/kg bodyweight [bw]). Also in dogs, no effect on respiratory functions was observed at the tested doses. Hyperglycaemia was observed in rats in acute and repeated dose studies. Fasted rats were less sensitive with a NOEL of 10 mg/kg body weight compared to fed rats with a NOEL of 1 mg/kg body weight. Mechanistic studies showed that emodepside inhibited secretory activities in mouse and rat β -cells of the pancreas presumably consistent with a mode of action through secretin receptors.

Emodepside showed no adverse effect on the ECG in anesthetized dogs. However, a moderate vasodilatation (reduction of total resistance, slight decrease of arterial blood pressure, moderate, probably reflex tachycardia) was observed at ≥1.5 mg/kg bw. A threshold plasma level of 0.1 µg/mL was determined for this effect. The significance of the vasodilatory effects is unclear as no effect on blood pressure or heart rate was seen in dogs following oral administration of emodepside for 4 weeks at up to 20 mg/kg bw.

Absorption, Distribution, Metabolism, Excretion (ADME)

In vitro studies showed moderate plasma protein binding of emodepside in all tested species with similar values in mice, dogs and human (fu 1.0 – 1.6%). In rats, gerbils and rabbits the fraction unbound was slightly higher (2.7% - 3.1%). The relevant Phase 1 biotransformation pathways of emodepside in humans as well as in animal species were oxidation with no significant species differences in terms of metabolic pathways. In humans, oxidative metabolism of emodepside was predominantly catalyzed by CYP3A4. The hydrolysis of the ester bonds was observed as an additional metabolic clearance pathway. Transport studies revealed a high permeability of Caco2-cells to emodepside as well as active efflux which was characterized as being P-glycoprotein mediated. Therefore, a role for P-glycoprotein in the pharmacokinetics of the compound cannot be excluded.

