4.2. Exclusion Criteria

The presence of any of the following will exclude a subject from study enrolment:

- 1. Participation in another clinical trial within 3 months prior and during the study, or 5-times the half-life of the drug tested in the previous clinical trial, whichever is longer (time calculated relative to the last dose in the previous clinical trial)
- Clinically relevant abnormal medical history, concurrent medical condition, acute or chronic illness or history of chronic illness sufficient to invalidate the subject's participation in the trial or make it unnecessarily hazardous.
- 3. Surgery (eg stomach bypass) or medical condition that might affect absorption of study drug taken orally.
- 4. Presence of abnormal physical findings, ECG, or laboratory values at the pre-trial screening assessment that could interfere with the objectives of the trial or the safety of the subject.

- Relevant pathological abnormalities in the ECG such as a second or thirddegree AV block, prolongation of the QRS complex over 120 msec or of the QTc-interval over 450 msec (QTcB or QTcF)
- 6. Blood pressure and heart rate in supine position at the screening examination outside one (or more) of the ranges:
 - 90–140 mm Hg systolic
 - 60-90 mm Hg diastolic
 - heart rate 40-100 beats/min

Subjects with vital signs outside the reference range for the population being studied may be included, at the investigator's discretion, if it is unlikely to introduce additional risk factors and will not interfere with study procedures.

- 7. History of relevant diseases of vital organs, of the central nervous system or other organs
- 8. Subjects with a medical or psychiatric disorder, condition or history of such that would increase the risk associated with study participation, or impair the subject's ability to participate or complete this study, in the opinion of the investigator or the sponsor
- 9. Subjects with a history of severe allergies, non-allergic drug reactions, severe adverse reaction to any drug, or multiple drug allergies
- 10. Subjects with a hypersensitivity to the investigational drug, the control agent and/ or to inactive constituents
- 11. Positive tests for hepatitis B & C, HIV
- 12. Subjects testing positive in the drug screening
- 13. Presence or history of drug or alcohol abuse during the last 10 years, or intake of more than 21 units of alcohol weekly.
- 14. Regular daily consumption of more than one liter of xanthine-containing beverages

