10.8.3. Hematology and Clinical Chemistry Parameters

Data from haematology and clinical chemistry will be summarised by treatment.

Any laboratory value outside the reference interval for that variable will be flagged with an 'H' if it is higher than the reference interval, and with an 'L' if it is lower. Additionally, if, during the course of the trial, a variable changes from baseline by more than a predetermined amount (as defined by the Principal Investigator), that value will receive a flag 'l' if increased, or 'D' if decreased. Therefore, if a value both falls outside the reference interval and alters from the baseline value by more than the predetermined amount, it will attract a double flag and will be considered to be potentially clinically important.

All laboratory values of potential clinical importance will be listed. In a separate listing, laboratory values of potential clinical importance will be listed with all related laboratory results (ie haematology or clinical chemistry). Frequencies of laboratory values of potential clinical importance will be summarised.

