## 10.4 Values of Potential Clinical Importance

Any laboratory value outside the reference interval for that variable will be flagged with an 'H' if it is higher than the reference interval, and with an 'L' if it is lower. Additionally, if, during the course of the trial, a variable changes from baseline (Day 0) by more than a predetermined amount (as defined by the Principal Investigator, Appendix A), that value will receive a flag 'I' if increased, or 'D' if decreased. Therefore, if a value both falls outside the reference interval and alters from the baseline value by more than the predetermined amount, it will attract a double flag and will be considered to be potentially clinically important.

A vital signs result will be considered to be of potential clinical importance if it falls outside the relevant range below:

Vital Sign	Range
Supine/semi-recumbent systolic blood pressure	85–160 mm Hg
Supine/semi-recumbent diastolic blood pressure	40–90 mm Hg
Supine/semi-recumbent heart rate	40–100 beats/min
Respiration rate	8–20 per min
Oral temperature	35.5–37.8°C

QTcB or QTcF > 450 msec and increases in QTcB or QTcF from baseline of > 30 msec will be considered to be potentially clinically important.

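### The Part 2 SAP flags supine vital signs by fixed range alone, so large individual changes can go unmarked, depending on baseline, and flagged subjects are not counted by treatment

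*Protocol*

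**What the plan says.** Protocol 10.8.1 gives no limits for vital signs; it says only "Vital signs of potential clinical importance will be listed separately". The limits are in SAP 10.4: "A vital signs result will be considered to be of potential clinical importance if it falls outside the relevant range below". The supine ranges there are 85–160 mmHg systolic, 40–90 mmHg diastolic and "40–100 beats/min" for heart rate.

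The other two importance rules use change from baseline.

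- **Laboratory values (Protocol 10.8.3, SAP 10.4):** a value qualifies "if a value both falls outside the reference interval and alters from the baseline value by more than the predetermined amount". The amounts are in SAP Appendix A.
- **QTc (Protocol 10.8.1, SAP 10.4):** a value above 450 msec and an increase above 30 msec are both criteria.

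The outputs differ too. Laboratory flags have a frequency table (SAP 12.5, Table 14.3.4), and ECG flags are counted by treatment and time point (SAP 12.6.2, Table 14.3.7.2). Vital-sign flags have a listing only (SAP 12.6.1, Listing 16.2.9.1).

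Entry limits at screening (Protocol 4.2, criterion 6) are "90–140 mm Hg systolic", "60-90 mm Hg diastolic" and "heart rate 40-100 beats/min". The investigator may admit subjects outside them. For Day 0 the baseline is that day's pre-dose value (SAP 10.2).

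**The concern.** A range rule depends on where the subject starts as well as on how far he moves. A subject who goes from 135/85 mmHg and 50 bpm to 95/55 mmHg and 95 bpm has changed by −40 mmHg, −30 mmHg and +45 bpm, and is not flagged on any of the three. A subject whose diastolic goes from 90 to 91 is flagged.

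This matters because safety is the primary objective and blood pressure is among the parameters recommended for monitoring (Protocol 1.4). Protocol 1.2 reports vasodilatation in anaesthetised dogs, with "slight decrease of arterial blood pressure, moderate, probably reflex tachycardia", above a plasma threshold of 0.1 µg/mL. Mean Cmax in Cohort 8 at 40 mg was 612 ng/mL (Protocol 1.3), about six times that threshold (612/100), and Cohort 10 repeats the dose. A fall in pressure with a rise in heart rate is a change within a subject. The flag, which exists to pick out individuals, is not built to detect it.

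**Working it through.** The plan states no figure for the largest unflagged change, so there is nothing to reproduce. The limits come from Protocol 4.2 and SAP 10.4.

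**1. Width of the ranges**

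| | Entry | Flag range | Width, flag vs entry |
|---|---|---|---|
| Systolic (mmHg) | 90–140 | 85–160 | 75 vs 50 (1.50×) |
| Diastolic (mmHg) | 60–90 | 40–90 | 50 vs 30 (1.67×) |
| Heart rate (bpm) | 40–100 | 40–100 | 60 vs 60 (1.00×) |

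**2. Largest unflagged change**

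Unflagged fall = baseline − lower flag limit. Unflagged rise = upper flag limit − baseline.

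- Systolic fall: 140 − 85 = 55; from 120, 35; from 90, only 5.
- Diastolic fall: 90 − 40 = 50; from 80, 40; from 60, 20.
- Heart-rate rise: 100 − 40 = 60; from 60, 40; from 80, 20.

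**3. Smallest flagged change from an entry edge, in whole units**

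- Diastolic: 1 upward (90 to 91), 21 downward (60 to 39).
- Heart rate: 1 at either end.
- Systolic: 6 downward (90 to 84), 21 upward (140 to 161).

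**4. How often a real systolic fall is flagged**

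The documents give no means or SDs. Assume a usual supine systolic of 120 (between-subject SD 8–10, limited to 90–140), within-subject SD 7 and independent errors.

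At a single reading, ignoring the truncation, P(flag) = Φ[(85 − (120 − fall))/√(SD² + 7²)]. For a 20 mmHg fall this is Φ(−15/10.63) = 0.08 with SD 8 and Φ(−15/12.21) = 0.11 with SD 10. With the truncation, simulation gives 8–11%, 17–21% and 32–35% for falls of 20, 25 and 30 mmHg.

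Now take a sustained 20 mmHg fall over several readings and count subjects flagged at least once. A 20 mmHg change limit serves purely as an illustration.

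- Six readings from 0.5 to 4 h (Protocol Table 3, which covers Cohort 9): range rule about 25–29%, change limit about 86%.
- Two readings, at 0.5 and 1 h, which are all that Cohort 10 has before 8 h (Protocol Table 5): range rule about 13–17% by the same simulation. The change limit gives 67%: the two differences share a baseline, so their correlation is 0.5 and P = 1 − (1/4 + 1/12) = 2/3.

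**5. Noise flags**

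- *Existing range rule, diastolic.* Assume a usual diastolic of 85, within-subject SD 5 and independent readings. Then P(recorded > 90) = 1 − Φ((90.5 − 85)/5) = 0.136 per reading. Over the 17 in-house post-dose readings of Table 3 this becomes 1 − 0.864^17 = 0.92; over the 12 of Table 5 it is 1 − 0.864^12 = 0.83. Over 17 readings it falls to 0.54 for a usual value of 82, 0.26 for 80 and 0.016 for 75.
- *Illustrative change limit, systolic.* With no drug effect and SD 7, one reading shows a fall of at least 20 with probability Φ(−20/(7√2)) = Φ(−2.02) = 0.022. By simulation, at least one such fall occurs in about 14–18% of subjects over 12–17 readings.

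**The case against.** Individual changes are already reported in several places. Template T_VS1 gives the minimum and maximum change by treatment and time point; with six active subjects per cohort, those are individual values. Tables 14.3.6.2 to 14.3.6.4 give AUC0-24 of change in supine diastolic pressure, systolic pressure and heart rate, as Day 0 minus Day −1 with a 95% CI. Individual profiles are plotted and complete listings produced. Clinically significant abnormalities become adverse events, which are tabulated by treatment. A reader might infer that large changes are invisible or never set against placebo; these outputs show otherwise.

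A reader might also infer that the flag range matches the entry range, or that a 55 mmHg fall is never flagged. The first holds for heart rate only. The second holds only from a baseline of 140 or higher: 36 mmHg from 120 and 6 mmHg from 90 are both flagged.

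The dog finding is not an established human effect. The same section calls its significance unclear, because four weeks of oral dosing in dogs showed no effect on pressure or heart rate.

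The laboratory precedent is imperfect. That rule requires out of range and changed, so it would not catch 135 to 95 either. Only QTc is a precedent for flagging change alone.

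Finally, a change flag adds noise, and a count compares six active subjects with two placebo subjects, since fed and fasted placebo are kept apart (SAP 9.1).

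All of this stands and limits the size of the point. It does not supply an output that marks an individual change as important or counts the subjects concerned.

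**Conclusion.** The gap is real but confined to the flag and its listing. SAP 10.4 gives vital signs no change criterion, unlike QTc and laboratory values, and no reason is stated. The 55 mmHg and 60 bpm figures are extremes from the edge of the entry range. They are not absolute maxima, because baseline is the pre-dose value and entry limits can be overridden. The more typical figures are 35 mmHg from 120 and 40 bpm from 60.

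The detection and noise rates rest on assumed SDs and independent readings and show order of magnitude only. A reader might infer that the range flag misses most affected subjects and mainly lists those with high-normal baselines. That depends on the size of the fall, the number of readings and the usual diastolic chosen. For a sustained 30 mmHg fall over six readings, the range rule flags roughly 63–65% of subjects at least once. The frequent diastolic noise flags arise near 85 and largely vanish at 75.

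The SAP supplied covers Part 2 only, so nothing is established for Part 1. This is a cheap improvement to descriptive safety reporting, in a study with no formal testing. It does not undermine the analysis.

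**What to change.** Keep the existing ranges. Add to SAP 10.4, for reporting only, a change-from-same-day-baseline flag for supine systolic pressure, diastolic pressure and heart rate.

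- **Baseline:** as in SAP 10.2, stating explicitly that the Day 0 pre-dose value also serves Days 1 to 7.
- **Limits:** set by the investigator before unblinding, as for Appendix A. The documents give no value; the 20 mmHg used above, and an equivalent 20 bpm, are illustrations only.
- **Display:** a separate flag in Listing 16.2.9.1, plus a small table of the number of subjects with each flag by treatment. Add a matching sentence to Protocol 10.8.1 if the protocol is next amended.
- **Reading the counts:** set them against the time-matched Day −1 readings and placebo, because some unaffected subjects will be flagged (about 14–18% for a systolic fall under the assumptions above).

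Suppressing range flags when the baseline was already out of range is not worth adding. For a usual diastolic of 85 it lowers the noise rate only from 0.92 to 0.92 × 0.864 = 0.79.

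The cost is a paragraph of SAP text, one table and a longer listing. All data are already collected, and the bedside repeat rules in Protocol 8.19.3 are not changed.
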